8.1.1. Primary endpoints for HZ/su and mRNA1273 booster study cohort

HZ/su immunogenicity post-dose 2 (anti-gE antibodies):

The immunogenicity of the HZ/su primary endpoint (Hypothesis 1) will be summarized on the HZ/su PPS.

Anti-gE antibody concentrations will be summarized at pre-vaccination (at Day 1 for HZ/suCoAd, at Week 2 for HZ/suSeq) and at 1 month post-dose 2 of HZ/su (at Week 14 for HZ/suSeq, at Week 12 for HZ/suCoAd), and expressed as a between-group GMC ratio at 1 month post-dose 2 of HZ/su. The geometric mean with 95% CI, geometric standard deviation along with median, minimum, maximum derived from the original data will be presented in the table. The geometric mean and geometric standard deviation calculations will be performed by taking the anti-log of the mean and standard deviation of the log10 transformed concentration data.

For anti-gE at 1 month post-dose 2 of HZ/su, the least square point estimate and its 95% CI of the between-group GMC ratios will be computed using an analysis of covariance (ANCOVA) model on the log10 transformation of the concentrations to demonstrate non-inferiority of the HZ/suCoAd vs. HZ/suSeq for the HZ/su immune response. The age strata (50-59, 60-69, ≥ 70 YOA) and pre-vaccination log-transformed antibody concentrations will be included as covariates and vaccine group will be included as a fixed effect.

Anti-gE antibody concentrations at all time points (pre-vaccination, 1 month post-dose 1 and 1 month post-dose 2) will be displayed using reverse cumulative curves.

mRNA-1273 booster immunogenicity (anti-S protein antibodies)

The immunogenicity assessment of the mRNA-1273 booster primary endpoint (Hypothesis 2) will be summarized on the mRNA-1273 PPS.

Anti-S Protein antibody concentrations will be summarized at pre-vaccination (Day 1) and at 1 month post mRNA-1273 booster dose (at Week 4 for both groups, HZ/suSeq and HZ/suCoAd), and expressed as a between-group GMC ratio at 1 month post mRNA-1273 booster dose. The geometric mean and geometric standard deviation by anti-log10 transformation, along with median, minimum, maximum derived from the original data will be presented in the table.

For anti-S Protein at 1 month post mRNA-1273 booster dose, the least square point estimate and its 95% CI of the between group GMC ratios will be computed using ANCOVA model on the log10 transformation of the concentrations to demonstrate non-inferiority of the HZ/suCoAd vs. HZ/suSeq for the HZ/su immune response. The age strata (50-59, 60-69, ≥ 70 YOA) and pre-vaccination log-transformed antibody concentrations will be included as covariates and vaccine group will be included as a fixed effect.

Pending final assay evaluations and validations prior to study specimen testing, anti-S protein may be replaced with SARS-CoV-2 neutralizing antibody titers in which case, GMT ratios will be used in the analysis described above.

8.1.2. Primary endpoints for Flu D-QIV and mRNA-1273 booster study cohort

Flu D-QIV immunogenicity (anti-HI antibodies)

The immunogenicity assessment of the Flu D-QIV primary endpoint (Hypothesis 3) will be summarized on the Flu D-QIV PPS.

Anti-HI antibody titers against each of 4 influenza strains included in Flu D-QIV will be summarized at pre-vaccination vaccination (at Day 1 for FluD-QIVCoAd, at Week 2 for FluD-QIVSeq) and at 1 month post Flu D-QIV (at Week 6 for FluD-QIVSeq, at Week 4 for FluD-QIVCoAd), and expressed as a between-group GMT ratio at 1 month post Flu D-QIV. The geometric mean and geometric standard deviation by anti-log10 transformation, along with median, minimum, maximum derived from the original data will be presented in the table.

To demonstrate non-inferiority of the FluD-QIVCoAd vs. FluD-QIVSeq for the Flu D-QIV immune response in terms of anti-HI antibody GMTs, the least square point estimate and its 95% CI of the between-group GMT ratios post-dose of Flu D-QIV will be computed using an ANCOVA model on the log10 transformation of the titers. The pre-vaccination log-transformed antibody titers and age strata (18-64, ≥ 65 YOA) will be included as covariates and vaccine group will be included as a fixed effect. This will be done for each of the 4 strains included in the Flu D-QIV vaccine.

mRNA-1273 booster immunogenicity (anti-S protein antibodies)

The immunogenicity assessment of the mRNA-1273 primary endpoint (Hypothesis 4) will be summarized for the mRNA-1273 PPS.

Anti-S Protein antibody concentrations will be summarized at pre-vaccination (Day 1) and at 1 month post mRNA-1273 booster dose (at Week 4 for FluD-QIVSeq and FluD-QIVCoAd) and expressed as a between-group GMC ratio at 1 month post mRNA-1273

booster dose. The geometric mean and geometric standard deviation by anti-log10 transformation, along with median, minimum, maximum derived from the original data will be presented in the table.

For anti-S Protein at 1 month post mRNA-1273 booster dose, the least square point estimate and its 95% CI of the between group GMC ratios will be computed using an analysis of covariance (ANCOVA) model on the log10 transformation of the concentrations to demonstrate non-inferiority of the FluD-QIVCoAd vs. FluD-QIVSeq for the Flu D-QIV immune response. The pre-vaccination log-transformed antibody concentrations and age strata (18-64, ≥ 65 YOA) will be included as covariates and vaccine group will be included as a fixed effect.

8.2. Secondary Immunogenicity Endpoint

Secondary objective for Flu D-QIV and mRNA-1273 booster cohort:

The secondary objective for the Flu D-QIV and mRNA-1273 booster cohort will be assessed once the primary objective for Flu D-QIV and mRNA-1273 booster cohort is demonstrated. This will not be used to confirm study success, rather, for informative purposes to support the primary endpoint.

Hypothesis 5: The null hypothesis for this secondary objective under consideration is UL of the 95% CI of the SCR difference between FluD-QIVSeq and FluD-QIVCoAd group at 1 month post Flu D-QIV (at Week 6 for FluD-QIVSeq, at Week 4 for FluD-QIVCoAd) is $\geq 10\%$.

Success criteria: The objective will be met if the UL of the 95% CI of the SCR difference between FluD-QIVSeq and FluD-QIVCoAd group at 1 month post Flu D-QIV (at Week 6 for FluD-QIVSeq, at Week 4 for FluD-QIVCoAd) is $< 10\%$ for each strain included in the Flu D-QIV vaccine.

8.2.1. Secondary Endpoints for Flu D-QIV immunogenicity (Anti-HI antibody SCRs)

The immunogenicity assessment of the Flu D-QIV secondary endpoint (Hypothesis 5) will be summarized for the Flu D-QIV PPS.

Anti-HI antibody SCRs against the 4 influenza strains will be summarized by group (FluD-QIVSeq and FluD-QIVCoAd) for the Flu D-QIV PPS.

To demonstrate non-inferiority of the FluD-QIVCoAd vs. FluD-QIVSeq for the Flu D-QIV immune response in terms of HI antibody SCRs for each strain, the difference between the SCR and the 95% CI for the difference in SCR in the FluD-QIVSeq group as compared to

the FluD-QIVCoAd group at 1 month post Flu DQIV (at Week 6 for FluD-QIVSeq, at Week 4 for FluD-QIVCoAd) will be evaluated.

The 2-sided 95% confidence interval (CI) on group difference in seroconversion rate will be computed based on the method of Miettinen and Nurminen (Miettinen, 1985). Descriptive immune endpoints

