Hypothesis 4: The null hypothesis for this primary objective under consideration is UL of 95% CI for adjusted GMC ratio between FluD-QIVSeq and FluD-QIVCoAd group for anti-S protein antibody concentration at 1 month post mRNA-1273 booster dose (at Week 4 for FluD-QIVSeq and FluD-QIVCoAd) is ≥ 1.5 .

Success criteria - The objective will be met if the UL of the 95% CI of the adjusted GMC ratio between FluD-QIVSeq and FluD-QIVCoAd group for anti-S protein antibody concentration at 1 month post mRNA-1273 booster dose (at Week 4 for FluD-QIVSeq and FluD-QIVCoAd) is <1.5.

Secondary objective for Flu D-QIV and mRNA-1273 booster cohort:

The secondary objective for the Flu D-QIV and mRNA-1273 booster cohort will be assessed once the primary objective for Flu D-QIV and mRNA-1273 booster cohort is demonstrated. This will not be used to confirm study success, rather, for informative purposes to support the primary endpoint.

Hypothesis 5: The null hypothesis for this secondary objective under consideration is UL of the 95% CI of the SCR difference between FluD-QIVSeq and FluD-QIVCoAd group at 1 month post Flu D-QIV (at Week 6 for FluD-QIVSeq, at Week 4 for FluD-QIVCoAd) is $\geq 10\%$.

Success criteria: The objective will be met if the UL of the 95% CI of the SCR difference between FluD-QIVSeq and FluD-QIVCoAd group at 1 month post Flu D-QIV (at Week 6 for FluD-QIVSeq, at Week 4 for FluD-QIVCoAd) is <10% for each strain included in the Flu D-QIV vaccine.

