9.3.5. Secondary immunogenicity endpoints analyses

9.3.5.1. Flu D-QIV immunogenicity (Anti-HI antibody SCRs)

The immunogenicity assessment of the Flu D-QIV secondary endpoint (Hypothesis 5 stated in Section 9.1) will be summarized for the Flu QIV and mRNA-1273 PPS

Anti-HI antibody SCRs against the 4 influenza strains will be summarized by group (FluD-QIVSeq and FluD-QIVCoAd).

To demonstrate non-inferiority of Flu D-QIV in terms of HI antibody SCRs for each strain, the difference between the SCR and the 95% CI for the difference in SCR in the FluD-QIVSeq group as compared to the FluD-QIVCoAd group at 1 month post Flu D-QIV (at Week 6 for FluD-QIVSeq, at Week 4 for FluD-QIVCoAd) will be evaluated.

The 2-sided 95% confidence interval (CI) on group difference in seroconversion rate will be computed based on the method of Miettinen and Nurminen [[Miettinen](#), 1985].

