4.1.2 Sample size for Flu D-QIV and mRNA-1273 booster study cohort

The non-inferiority of Flu D-QIV using GMTs (hypothesis 3, see Section 8.1) will be tested with a 1-sided type I error of 0.025 for all 4 strains in the Flu D-QIV vaccine. No adjustment is needed for the type I error due to multiple comparison of Flu D-QIV 4 strains since one wants to reject the null hypothesis if one comparison is not conclusive.

The non-inferiority of Flu D-QIV using SCR difference for 4 strains (Flu D-QIV and/mRNA-1273 booster cohort secondary endpoint, hypothesis 5, see Section 8.2) will be tested using a sequential approach, meaning, hypothesis 3 and 4 (GMT, Flu D-QIV and mRNA-1273 booster primary endpoint), see Section 8.1, must be tested and non-inferiority of Flu D-QIV and mRNA-1273 booster using GMT ratio must be demonstrated before hypothesis 5 (see Section 8.2) is tested. Both tests will use a type I error of 0.025. Study success on the Flu D-QIV and mRNA-1273 booster cohort will be declared if hypothesis 3 and 4 (see Section 8.1) is rejected. Therefore, the power to achieve success for Flu D-QIV and mRNA-1273 booster cohort is driven by primary objectives for the Flu D-QIV and mRNA-1273 booster cohort.

A GMC ratio of 1.1 between FluD-QIVSeq and FluD-QIVCoAd is assumed for the mRNA endpoint. A GMT ratio of 1.04 between FluD-QIVSeq and Flu D-QIV is assumed for the flu endpoint. The global power considers meeting both primary objectives in the Flu D-QIV and mRNA-1273 booster cohort - with 450 evaluable participants in the FluD-QIVCoAd and FluD-QIVSeq groups, the global power is approximately 90.9%.

The nominal power for the secondary objective to demonstrate non-inferiority in terms of SCR difference for each strain in the Flu D-QIV vaccine between FluD-QIVSeq and FluD-QIVCoAd groups is at least 85%. Assuming 10% of the participants randomized are non-evaluable (e.g. due to drop out/protocol violation), approximately 1000 participants will need to be randomized (500 participants each in the FluD-QIVCoAd and FluD-QIVSeq groups).

Sample size calculations for the Flu D-QIV and mRNA-1273 booster study cohort can be found in Table 4.

Table 4 Sample size calculations for Flu D-QIV and mRNA-1273 booster study cohort

Primary Endpoint	Number of Evaluable Participants per Group	α	Standard Deviation	Reference δ Assumed	NI δ	Total β	Power
FLU D-QIV Non-inferiority* (1-sided test) – 4 Strains – Primary Endpoint on GMT ratio							

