4.2. Randomization and Stratification

Within each cohort, participants will be centrally randomized in a 1:1 ratio to 1 of the 2 study groups (sequential or co-administration) and receive a Randomization Number through Interactive Response Tool (IRT). At randomization, the IRT system will validate the participant's age. Participants in the HZ/su and mRNA-1273 booster cohort will be stratified by age group (50 to 59 YOA, 60 to 69 YOA, and ≥ 70 YOA) prior to randomization. Participants in the Flu D-QIV and mRNA-1273 booster cohort will also be stratified by age group (18 to 64 YOA and ≥ 65 YOA) prior to randomization. Randomization will be set to ensure at least 69 participants per group will be assigned to the ≥ 70 YOA stratum in the HZ/su and mRNA-1273 booster cohort and at least 75 participants per group will be targeted for assignment to the ≥ 65 YOA stratum in the Flu D-QIV and mRNA-1273 booster cohort.

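### The Hypothesis 5 interval for the seroconversion-rate difference does not use the age strata by which the Flu cohort is randomised: a small improvement to make, not an error

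*SAP*

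**What the plan says.** SAP 8.2.1 sets the method for Hypothesis 5: the two-sided 95% interval for the SCR difference "will be computed based on the method of Miettinen and Nurminen". Protocol 9.3.5.1 says the same, an interval "computed based on the method of Miettinen and Nurminen". Neither place mentions strata, weights or covariates. The footnote to the SCR power table (SAP 4.1.2, Table 4) cites a test for two independent proportions, which fits an unstratified analysis.

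The randomisation does use age. SAP 4.2 states: "Participants in the Flu D-QIV and mRNA-1273 booster cohort will also be stratified by age group", the groups being 18-64 and 65 and over. SAP 8.1.2 puts those strata into the ANCOVA models for Hypothesis 3 (HI titres) and Hypothesis 4 (anti-S).

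Hypothesis 5 succeeds only if the upper limit for the SCR difference, sequential minus co-administered, "is <10% for each strain included in the Flu D-QIV vaccine" (Protocol 9.1). It is tested only after Hypotheses 3 and 4 have succeeded (SAP 4.1.2). Protocol 9.1 and SAP 8.2 describe it as supportive and not part of the criterion for study success.

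**The concern.** Hypotheses 3 and 5 rest on the same HI titres at the same visits in the same per-protocol set. One comparison is adjusted for the randomisation factor and the other is not, and no reason is given.

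Two things could be lost:

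- **Precision.** If SCR differs by age, the unstratified variance includes a between-stratum part that stratification removes. All four strains must pass, and the two B strains have the lowest stated power, 85.1% and 86.0%.
- **Protection against imbalance.** Stratified randomisation balances age among those randomised. The test is run on the PPS, where exclusions can differ by group. SAP Table 9 lists three PPS-relevant visit windows for the sequential group and one for the co-administration group. Qualification is per vaccine, so not all of these need bear on the Flu D-QIV PPS.

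The planned age-subgroup summaries (SAP 8, 8.2.2.3) will show SCR by age. They do not give one age-adjusted difference to set against the 10-point margin.

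**Working it through.** **Inputs from the documents**

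- 450 evaluable per group (SAP 4.1.2: "with 450 evaluable participants in the FluD-QIVCoAd and FluD-QIVSeq groups, the global power is approximately 90.9"%). With "Assuming 10% of the participants randomized are non-evaluable", 450 / 0.9 = 500 randomised per group.
- One-sided alpha 0.025 (SAP 4.1.2: "Both tests will use a type I error of 0.025"), margin 10 percentage points, true difference taken as 0.
- Assumed overall SCR by strain, from SAP Table 4.
- Share aged 65 or over: w = 75/500 = 15%. This is the target minimum in SAP 4.2; the actual share is not given.

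**Input not in the documents.** The SCR gap d between the age strata is assumed to be 0, 10, 20 or 30 points.

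**Step 1. Reproduce the stated power.** Power = Φ(0.10 / √(2p(1−p)/450) − 1.96). For B/Victoria:

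- p(1−p) = 0.538 × 0.462 = 0.24856
- standard error = √(2 × 0.24856/450) = 0.03324
- 0.10/0.03324 − 1.96 = 1.049, so power is 85.3%
- interval half-width = 1.96 × 0.03324 = 6.51 points

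| Strain | SCR | Stated power | Formula above | Restricted-likelihood variance |
|---|---|---|---|---|
| A/H1N1 | 78.6% | 95.5% | 95.5% | 95.4% |
| A/H3N2 | 70.3% | 90.8% | 90.7% | 90.8% |
| B/Victoria | 53.8% | 85.1% | 85.3% | 85.5% |
| B/Yamagata | 56.9% | 86.0% | 85.8% | 86.0% |

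The stated figures reproduce to within 0.4 points. They are correct for an unstratified test.

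**Step 2. Remove the between-stratum variance.** With the overall SCR held fixed, the within-stratum variance is p(1−p) − w(1−w)d². At w = 0.15, w(1−w) = 0.1275. For B/Victoria:

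| Age gap d | Variance | Reduction | Half-width (points) | Power |
|---|---|---|---|---|
| 0 | 0.24856 | 0% | 6.51 | 85.3% |
| 10 points | 0.24728 | 0.5% | 6.50 | 85.5% |
| 20 points | 0.24346 | 2.1% | 6.45 | 86.0% |
| 30 points | 0.23708 | 4.6% | 6.36 | 86.9% |

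Across the four strains the gain in power is 0.13 to 0.18 points at a 10-point gap, 0.5 to 0.7 at 20 and 1.1 to 1.6 at 30. If 30% were aged 65 or over (an assumption), B/Victoria power would be 85.6%, 86.5% or 87.9%.

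**Step 3. All four strains.** If the strains were independent (an assumption), power to pass all four is 0.9552 × 0.9070 × 0.8529 × 0.8575 = 63.4% unstratified. At 15% aged 65 or over and a 20-point gap it becomes 65.2%.

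**Step 4. Check by simulation.** In 100,000 simulated trials per scenario, with 15% aged 65 or over and stratum-size weights, stratifying added 0.05 to 0.3 points of power at a 10-point gap, 0.2 to 1.1 at 20 and 0.5 to 1.4 at 30. One-sided type I error of the unstratified test was 2.3-2.6% at gaps of 0 to 10 points and about 2.2% at 30. For the stratified test it was 2.3-2.6% throughout.

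**Step 5. Imbalance.** As an illustration with assumed values, a 3-point difference between groups in the share aged 65 or over, with a 20-point age gap, shifts the crude difference by 0.03 × 20 = 0.6 points. A stratified estimate removes that shift.

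**The case against.** The case for leaving the plan alone is strong on size. At a 10-point gap and 15% aged 65 or over, the half-width moves from 6.51 to 6.50 points. Hypothesis 5 is gated and does not decide study success. The share aged 65 or over may fall short of 15%: the amendment softened the 75 per group to a target because many older candidates might already have had their influenza vaccine. SCR is a binary endpoint with baseline titre built into its definition, so it need not follow the ANCOVA model. All of this stands, and it keeps the point minor.

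A reader might take the CBER criteria in SAP 8.2.2.3 (lower limit for SCR at least 40% in those aged 18-64, 30% in those 65 and over) as evidence of an age gap. They are acceptance limits, not estimates of SCR, so the gaps used here remain assumptions. Likewise, the documents show no age imbalance in the PPS. They show only that the randomisation does not guarantee balance there.

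The objection does not supply a reason for leaving out the randomisation factor, and the age-subgroup tables do not provide an adjusted test.

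**Conclusion.** The Hypothesis 5 interval, as written, does not use the age strata of the randomisation, while the analyses of Hypotheses 3 and 4 do. Bringing them into line is worthwhile but small. At 15% aged 65 or over, B/Victoria power rises from 85.3% to between 85.5% and 86.9% for assumed age gaps of 10 to 30 points, and not at all if there is no gap. Consistency with the randomisation and protection against imbalance in the PPS weigh at least as much as the precision.

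A reader might infer that the planned interval is invalid, that the power table is wrong, or that success of the Flu cohort is at risk. The documents support none of these. The simulated error rate is close to nominal or slightly conservative, the stated power reproduces, and cohort success depends on Hypotheses 3 and 4 only.

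**What to change.** In SAP 8.2.1, specify that the SCR difference and its two-sided 95% CI for each strain are computed by the Miettinen-Nurminen method stratified by randomisation age group (18-64, 65 and over). State the stratum weights, for example proportional to stratum size. Keep the unstratified interval as a sensitivity analysis. If the sponsor prefers the unstratified interval as the main one, say so explicitly and give the reason.

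The cost is a sentence or two of SAP text and minor programming, with no new data and no change in sample size. The one real drawback is that the weights must be fixed in advance and, if the group difference varies by age, they affect what is estimated. As the study is open-label, the choice should be recorded before the immunogenicity data are analysed.

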8.2.2.1 Anti-gE humoral immunogenicity at pre-vaccination and post-dose 2 of HZ/su

Descriptive statistics (including 95% CIs) of the following anti-gE humoral immunogenicity parameters will be provided by group and by age strata (50-59, 60-69, \geq 70 YOA) at baseline and at 1 month post-dose 2 of HZ/su (at Week 14 for HZ/suSeq, at Week 12 for HZ/suCoAd) for the HZ/su PPS.

- VRR with exact 95% CI at 1 month post-dose 2 of HZ/su
 - The VRR for anti-gE post-dose 2 is defined as the percentage of participants who have at least:
 - 4-fold increase in the post-dose anti-gE antibody concentration as compared to the pre-vaccination anti-gE antibody concentration, for participants who are seropositive at pre-vaccination, or,
 - A 4-fold increase in the post-dose anti-gE antibody concentration as compared to the anti-gE antibody cut-off value of 97 mIU/mL for seropositivity, for participants who are seronegative at pre-vaccination.

This will be summarized by participants who are seronegative at pre-vaccination, seropositive at pre-vaccination and overall status at pre-vaccination (seronegative or seropositive).

- Seropositivity rate with exact 95% CI at pre-vaccination (at Day 1 for HZ/suCoAd, at Week 2 for HZ/suSeq) and at 1 month post-dose 2 of HZ/su (at Week 14 for HZ/suSeq, at Week 12 for HZ/suCoAd). Seropositivity is defined as the percentage of participants whose anti-gE antibody concentration is greater than or equal to the assay cutoff value (97 mIU/mL).
- Anti-gE antibody concentrations expressed as GMC with 95% CI at pre-vaccination (at Day 1 for HZ/suCoAd, at Week 2 for HZ/suSeq) and at 1 month post-dose 2 of HZ/su (at Week 14 for HZ/suSeq, at Week 12 for HZ/suCoAd). GMC calculations will be performed by taking the anti-log of the mean of the log concentration transformations. Anti-gE antibody concentrations at all time points (pre, Dose 1 and Dose 2) will be displayed using reverse cumulative curves.
- MGI in anti-gE antibody from pre-vaccination with 95% CI at 1 month post-dose 2 of HZ/su (at Week 14 for HZ/suSeq, at Week 12 for HZ/suCoAd).

- Descriptive statistics of fold increase from baseline for anti-gE antibody enzyme linked immunosorbent assay (ELISA) concentrations.
- The distribution of the fold increase in anti-gE antibody ELISA concentrations i.e. percentage of participants with a more than X-fold (e.g. >2, >4, >6,...-fold) increase along with 95% CI will be presented.

8.2.2.2 mRNA-1273 booster dose humoral immunogenicity

Descriptive statistics (including 95% CIs) of the following mRNA-1273 booster immunogenicity parameters will be provided by group and by age strata (50-59, 60- 69, \geq 70 YOA for HZ/su and mRNA-1273 booster cohort; 18-64 and \geq 65 YOA for Flu DQIV and mRNA-1273 booster cohort). All summaries will be provided for the mRNA-1273 PPS by cohort.

- Anti-S Protein antibody concentrations expressed as GMC with 95% CIs by group at pre-vaccination (Day 1) and 1 month post mRNA-1273 booster dose (at Week 4 for all groups including HZ/suSeq, HZ/suCoAd, FluD-QIVSeq, FluD-QIVCoAd and overall). The GMC calculations will be performed by taking the anti-log of the mean of the log concentration transformations. Anti-S protein antibody concentrations will be displayed using reverse cumulative curves.
- MGI with 95% CI at 1 month post mRNA-1273 booster dose (at Week 4 for all groups).

